### **6.11 Training of Research Coordinators and Occupational Therapists.**

[name] will oversee training of the Research Coordinator and Occupational Therapists that are compulsory prior to the study staff initiating contact with participants as it relates to this study. [name] must sign off on their training and maintain documentation of training through the course of the study. Details of the training are provided in the MOOP (Section 6.2).

## ***7.0 Study Intervention Discontinuation/ Participant Discontinuation / Withdrawal***

### **7.1 Participant Withdrawal**

Participants may withdraw voluntarily from the study. In addition, participants may discontinue the study intervention, but remain in the study for follow-up if he/she wishes. A dedicated Case Report Form (CRF) administered on RedCap entitled "Withdrawal Form" will be completed by our research coordinator to capture the date and the specific underlying reason for discontinuation of study intervention or participant discontinuation/withdrawal.

## **7.2 Discontinuation of Study Intervention**

The PI may discontinue a participant from the study for the following reasons:

- Inability to fit the hand orthosis after a good will effort by the participant and our OT.
- Pregnancy
- If any clinical adverse event (AE) occurs such that continued participation in the study would not be in the best interest of the participant
- If early termination of the study is deemed necessary

At the time that the orthosis is created and customized for the participant, our OT will provide instruction on how to don the orthosis and how to remove the orthosis. She will also provide instruction to the participant that if the finger trap is uncomfortable and difficult to remove, there is always the option of cutting the finger trap off the finger with a pair of scissors. Our OT will observe the participant donning and removing the orthosis in the clinical setting to verify that the participant has good understanding of how to perform these activities. She will also review with the participant how to cut the finger trap off in the setting that the participant is unable to remove the finger trap. She will also provide the participants with a handout describing these activities that participants can take with them. If the participants still have difficulty donning and/or removing the orthoses, the participants will be instructed to contact our OT to schedule an as needed appointment to review how to perform these activities.

We will do our best to minimize any discomfort related to these orthoses as our OT will make every effort to address any discomfort the participants may complain of at the time that the orthoses are created by modifying or adjusting the orthoses. Also, we will schedule all participants to return for a 2 and 4 week follow up visit with our OT to assess for appropriate fit and to address any concerns the participants might have related to the orthoses. If these issues cannot be satisfactorily resolved, then the participants will be given an option to terminate use of the orthosis.

Discontinuation from the study intervention does not mean discontinuation from the study, and remaining study procedures will be completed as indicated by the study protocol. If a clinically significant finding is identified (including, but not limited to changes from baseline) after enrollment, the investigator or qualified designee will determine if any change in participant management is needed. Any new clinically relevant finding will be reported as an adverse event (AE).

A dedicated Case Report Form (CRF) administered on RedCap entitled “Early Termination Form” will be completed by our research coordinator to capture the date and the specific underlying reason for termination from study intervention.

Subjects who sign the informed consent form and are randomized but do not receive the study intervention will still be included in the baseline demographics description. Missing outcomes among participants who missed pain and function questions or lost to follow up will be addressed by multiple imputation using the Markov chain Monte Carlo method. Under the assumption of missing at random, we will include factors which may be related to missing of outcome in the imputation, such baseline demographic characteristics, disease severity, etc. We can use this method of imputation because all outcomes are continuous and they can be assumed to follow multivariate normality distribution. To use this method of multiple imputations, there is an assumption of missing at random. Though this assumption is not testable, multiple imputation method are viewed as less biased than a completers’ analysis, last observation carried forward, and single imputation method. Subjects who sign the informed consent form, and are randomized and receive the study intervention, and subsequently withdraw, or are withdrawn or discontinued from the study, will not be replaced.

### **7.3 Lost-to-Follow-up**

A participant will be considered **lost to follow-up** if he or she fails to return for the final 24 week follow up visit and is unable to be contacted by the study site staff.

The following actions must be taken if a participant fails to return to the clinic for a required study visit:

- The site will attempt to contact the participant and reschedule the missed visit within 14 days and counsel the participant on the importance of maintaining the assigned visit schedule and ascertain if the participant wishes to and/or should continue in the study.
- Before a participant is deemed lost to follow-up, the investigator or designee will make every effort to regain contact with the participant (where possible, 3 telephone calls and, if necessary, a certified letter to the participant's last known mailing address). These contact attempts should be documented in the participant's study file.
- Should the participant continue to be unreachable, he or she will be considered to have withdrawn from the study with a primary reason of lost to follow-up.

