At 2 weeks of follow up, we will have the participant return to the clinic setting with the OT to verify correct orthosis application and to provide any necessary adjustments to the orthosis. To provide comparable attention to the control group, we will also ask those participants to bring their resting hand orthoses to assess correct application of the orthoses and provision of any necessary adjustments.

The most symptomatic DIP will be fitted with a finger trap. Additionally, our OT will also ask the participant if there are other joints which he/she would like to also be fitted with a finger trap. We will have a variety of sizes of finger traps available at the time of fitting. Each finger that will be fitted with a trap will be sized for an appropriately sized finger trap that will be snug but easily removed by the participant.

Using a heat gun, our OT will heat and roll a slot at the distal edge of the orthosis to accommodate the center of each of the finger traps. Then, with each finger trap applied, the end of the traction device loop will be marked on the posterior surface of the orthosis. Our OT will perforate a hole in the orthosis at the end of the traction device length and insert a rubber band post upon which the loop of the finger trap will be applied. A Velcro attachment will be applied to maintain appropriate tension of the finger traps. Padding will be placed over the band after attachment on the volar orthosis surface.

***The participants will be asked to put their orthoses in opaque traveling bags when transporting them. And at home, they are asked to store their orthoses in a clean, dry area, at room temperature when the orthoses are not being worn.***

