## **8.2. Symptom Efficacy Assessments**

All of the following assessments will be made by our Research Coordinator and itemization of the data will be collected in RedCap. These will include:

Outcomes: (Assessed at the baseline, week 4, week 12, and week 24 visits)

- the VAS pain scale, asking about pain in the hand that includes the most symptomatic DIP over the last 48 hours (primary outcome)
- Australian Canadian Hand OA Index (AUSCAN) pain scale, (although we have requested copyright permission to use the scale, we have yet to receive permission to do so – we plan to administer the outcome, but if not given permission, we will not publish with this data).
- the VAS pain scale, asking about pain in the most symptomatic DIP in the last 48 hours,
- the AUSCAN function subscale,
- the Functional Index for Hand Osteoarthritis (FIHOA)
- the Disabilities of the Arm, Shoulder, and Hand (DASH),
- the Michigan Hand Outcomes,
- the Functional Dexterity Test,
- grip and pinch strength, and
- tenderness on joint palpation on all hand joints.
- photographs of the participant's hands
- We will also take a medication inventory (dichotomous assessments)
  - i. Pain medications (e.g. acetaminophen, all non-steroidal anti-inflammatory medications, and opioid medications).
  - ii. Glucosamine and chondroitin
  - iii. Marijuana use

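### Section 7.3 gives loss to follow-up two triggers and no closing date, so an unreachable participant may be withdrawn well before week 24, when the only follow-up radiograph is due

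*Combined protocol and SAP*

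**What the plan says.** Section 7.3 opens by defining the term, which covers anyone who "fails to return for the final 24 week follow up visit and is unable to be contacted by the study site staff". Both conditions are needed, and the visit concerned is the last one.

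The list beneath has a wider trigger: "The following actions must be taken if a participant fails to return to the clinic for a required study visit". It has three steps:

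- The site tries to make contact and "reschedule the missed visit within 14 days".
- "Before a participant is deemed lost to follow-up, the investigator or designee will make every effort to regain contact with the participant", by three telephone calls where possible and a certified letter if needed.
- "Should the participant continue to be unreachable, he or she will be considered to have withdrawn from the study", with loss to follow-up as the main reason.

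Only the first step carries a time limit.

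Clinic visits after baseline fall at weeks 2, 4, 12 and 24 (Section 4.3.a). The week-2 visit is for everyone: "At 2 weeks of follow up, we will have the participant return to the clinic setting with the OT" (Section 6.5). Symptom outcomes, including the primary hand pain score, are "Assessed at the baseline, week 4, week 12, and week 24 visits" (Section 8.2). Hand radiographs are taken only at baseline and week 24 (Section 8.4.i).

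Sections 7.1 and 7.2 keep people who stop the orthosis in follow-up. No section says the same of people recorded as withdrawn from the study.

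**The concern.** One label has two triggers. Under the definition, someone who misses week 4 and cannot be reached is not yet lost to follow-up, because the final visit has not come round. Under the action list, the same person can be recorded as withdrawn for loss to follow-up as soon as the contact attempts have failed. The Withdrawal Form (Section 7.1) needs a date and a reason, and 7.3 does not settle which date applies. Two coordinators could code the same history differently.

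The coding matters because withdrawal from the study appears to end follow-up, and nothing in 7.3 calls for another attempt at week 24 before it is recorded. The primary structure endpoint, the 24-week change in summed Kellgren and Lawrence scores in the braced hand, has no measurement between baseline and week 24. A participant closed early has no outcome for it, and the value can only be imputed, under a missing-at-random assumption that Section 9.0 itself says cannot be tested. In a trial of 40, a loss that better wording might prevent is worth preventing.

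**Working it through.** The plan states no figure for loss to follow-up, so there is none to reproduce. The power statement in Section 9.0 does not bear on this point. The check has two parts: how early closure could fall, and what data would remain.

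**Inputs.** Visit days and windows come from the Schedule of Activities (Section 1.1): day 14 ± 7, day 28 ± 7, day 84 ± 14 and day 168 ± 14. The day-84 column is headed as a reminder visit, but Section 4.3.a lists week 12 as a study visit with all clinical assessments. The 14 days come from the first step of the list in 7.3.

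**Assumption.** Withdrawal is recorded when the 14-day rescheduling period ends. Section 7.3 does not say this. It is used only because no other period is given.

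**Formulas.**
- Nominal closing day = visit day + 14. Gap = 168 − closing day.
- Late closing day = visit day + window + 14. Gap = 168 − late closing day.

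| Missed visit | Nominal closing day | Gap to day 168 | Late closing day | Gap to day 168 |
|---|---|---|---|---|
| Week 2 | 14 + 14 = 28 | 140 days, 20 weeks | 14 + 7 + 14 = 35 | 133 days, 19 weeks |
| Week 4 | 28 + 14 = 42 | 126 days, 18 weeks | 28 + 7 + 14 = 49 | 119 days, 17 weeks |
| Week 12 | 84 + 14 = 98 | 70 days, 10 weeks | 84 + 14 + 14 = 112 | 56 days, 8 weeks |

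The range to the nominal final visit is therefore 8 to 20 weeks. Measured from the late closing day to the earliest permitted final visit (168 − 14 = day 154), the gaps are 119, 105 and 42 days, or 17, 15 and 6 weeks. Each further week spent on calls or a letter shortens every gap by one week. The final window closes on day 168 + 14 = 182.

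**What remains if the participant is closed early.**
- After a missed week 2 or week 4 visit: baseline pain only, and no follow-up radiograph.
- After a missed week 12 visit: baseline pain, week-4 pain if that visit was attended, and no follow-up radiograph.

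Pain scores already collected would enter the repeated-measures model in Section 9.0. The radiographic endpoint would be wholly missing in every case.

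**The case against.** The strongest reply is that 7.3 should be read as a whole. The 14 days govern only the rescheduling attempt, and no step sets a closing date. The second and third steps both use the term that the opening sentence ties to the final visit. On that reading, contact attempts begin after any missed visit, but the label waits until week 24. This is a fair reading, and it defeats any claim that the protocol requires withdrawal at day 42 or day 98. It does not remove the ambiguity: the last step sits in a list triggered by any required visit, and nothing in it says to wait.

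A missed visit alone is also not enough. The participant must stay unreachable after the calls and, if needed, the letter. Weekly contact by email, text or telephone (Section 6.10) and reminders before visits (Section 5.5) give further chances, and nothing bars someone who reappears from attending week 24. All this stands, and it suggests that few people would be affected.

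Multiple imputation is planned for missing data. That is true, but for the radiograph it would have no interim measurement to draw on.

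Two stronger inferences are tempting and not supported:

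- A reader might infer that early withdrawals would distort the pilot's feasibility results. The withdrawal proportion in Section 10.10.a belongs to the monitoring reports. It is not among the measures listed for the feasibility aim in Sections 3.0 and 9.0.
- A reader might infer that the 14-day rescheduling period creates extra protocol deviations at weeks 2 and 4. Section 10.1 already counts a missed clinic visit as a deviation, and a late visit at least recovers data.

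**Conclusion.** The point holds as an inconsistency in 7.3 that permits, but does not clearly require, withdrawal before week 24. If closure follows the 14-day rescheduling period, it could come about 8 to 20 weeks before day 168. That timing is an assumption. The mismatch between the definition and the trigger of the list is in the text.

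For a participant closed early, the radiographic loss is complete and the symptom loss is partial when an earlier score exists. A reader might go on to put a percentage on the avoidable loss in each arm. The documents give no rate of unreachable participants, and not everyone who ignored calls and a letter would have returned for week 24, so no such figure is offered. This is a modest weakness, worth correcting because the correction is cheap.

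**What to change.** Amend 7.3 to state that:

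- an unreachable participant who misses week 2, 4 or 12 is recorded as having a missed visit;
- the weekly contacts continue and the week-24 appointment is kept;
- the withdrawn, lost-to-follow-up status is assigned only once the week-24 window has closed (day 182) without contact;
- withdrawal of consent is recorded separately, when it happens.

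This makes the list agree with the section's own definition. It costs a few sentences, some extra messages to non-responders, and later status coding for a few participants.

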## ***8.0 Study Assessments***

### **8.1 Justification of Objectives and Endpoints**

OBJECTIVES	ENDPOINTS	JUSTIFICATION FOR ENDPOINTS
Primary		
The primary symptom objective is to assess whether traction therapy plus standard of care treatment for nodal OA reduces symptoms more than standard of care treatment that includes a resting hand splint.	The primary symptom endpoint will be pain as assessed on a visual analog scale (VAS) in the more symptomatic hand that includes the most symptomatic DIP joint by 24 weeks of use of traction therapy with standard of care treatment for hand OA to establish efficacy of traction therapy.	This outcome measure has been recommended by the OARSI Clinical Trials Recommendations: Design and conduct of clinical trials for hand osteoarthritis.  It has also been supported by the Update of OMERACT Hand OA Outcomes. 
The primary structure objective is to assess whether traction therapy plus standard of care treatment for nodal OA reduces structural progression compared with standard of care treatment that includes a resting hand splint.	The primary structure endpoint will be change in sum of the Kellgren and Lawrence score  of all DIPs in the hand that was braced over 24 weeks.	The use of radiographic imaging as a means of measuring structural outcome has been recommended by the OARSI Clinical Trials Recommendations: Design and conduct of clinical trials for hand osteoarthritis.  Although there are

OBJECTIVES	ENDPOINTS	JUSTIFICATION FOR ENDPOINTS
		limitations to the use of Kellgren and Lawrence scoring which was first described in 1957, currently there are no agreed upon alternatives to this scoring strategy.
Secondary		
The secondary symptom objectives are to assess whether traction therapy plus standard of care treatment for nodal OA reduces symptoms more than standard of care treatment that includes a resting hand splint using alternative hand symptom and function outcomes.	
The secondary symptom endpoint will be pain and function in the more symptomatic hand that includes the most symptomatic DIP joint by 24 weeks of use of traction therapy with standard of care treatment for hand OA to further support efficacy of traction therapy. These outcomes will include:
 
 
• The Functional Index for Hand Osteoarthritis (FIHOA)
 
• The Disabilities of Arm Shoulder and Hand (DASH)
 
• The Functional Dexterity Test
 
• Grip strength
 
• Pinch strength
 
• Tenderness on joint palpation.
 
	As this is a pilot study, we are making an attempt to include other measures that might also be of relevance and may perhaps be more useful in the follow up study to this pilot.
The secondary structure objectives are to assess whether traction therapy plus standard of care treatment for nodal OA reduces structural progression compared with standard of care treatment that includes a resting hand splint.	
The secondary structure endpoints will be change in sum of the following scores all DIPs in the hand that was braced over 24 weeks:
 
 
• joint space narrowing
 
• osteophyte scores
 
• Verbruggen-Veys scores
 
	Although a 24 week follow up time period might be too short to see a difference in the treatment arms, it is worth a look at the different radiographic features of OA to see if they are different between the two treatment arms.
Tertiary/Exploratory		

OBJECTIVES	ENDPOINTS	JUSTIFICATION FOR ENDPOINTS
The tertiary / exploratory structure objective is to assess whether traction therapy plus standard of care treatment for nodal OA modifies features of OA seen on MRI more compared with standard of care treatment that includes a resting hand splint.	
The exploratory endpoints include measurement in the most symptomatic DIP:
 
 
• collateral ligament thickening
 
• enthesial bone marrow edema
 
• erosions
 
 
Because this is a pilot study and we only had limited funds to obtain MRIs, we are only evaluating these changes on 5 people in each treatment arm.
	
Prior observational studies indicated that there is pathology in these structures visualized on MRI. Perhaps these might change over a shorter period of time than radiographs. If there is a signal with these measures then we might include MRI for all participants for the follow up clinical trial.

The tertiary / exploratory clinical assessment objective is to evaluate whether traction therapy plus standard of care treatment for nodal OA modifies visual appearance of Heberden's nodes using photographs compared with standard of care treatment that includes a resting hand splint.	Visual inspection of the digital photographs for differences in erythema of the most symptomatic DIPs.	
This is a low risk outcome measure. Although it is not currently viewed as a standard outcome measure, if we can show this is a useful outcome measure this might serve as preliminary evidence to use this in our follow up study.

Table 3. Study Objectives, Endpoints, and the Justification of those Endpoints.

## **8.2. Symptom Efficacy Assessments**

All of the following assessments will be made by our Research Coordinator and itemization of the data will be collected in RedCap. These will include:

Outcomes: (Assessed at the baseline, week 4, week 12, and week 24 visits)

- the VAS pain scale, asking about pain in the hand that includes the most symptomatic DIP over the last 48 hours (primary outcome)
- Australian Canadian Hand OA Index (AUSCAN) pain scale, (although we have requested copyright permission to use the scale, we have yet to receive permission to do so – we plan to administer the outcome, but if not given permission, we will not publish with this data).
- the VAS pain scale, asking about pain in the most symptomatic DIP in the last 48 hours,
- the AUSCAN function subscale,
- the Functional Index for Hand Osteoarthritis (FIHOA)
- the Disabilities of the Arm, Shoulder, and Hand (DASH),
- the Michigan Hand Outcomes,
- the Functional Dexterity Test,
- grip and pinch strength, and
- tenderness on joint palpation on all hand joints.
- photographs of the participant's hands
- We will also take a medication inventory (dichotomous assessments)
  - i. Pain medications (e.g. acetaminophen, all non-steroidal anti-inflammatory medications, and opioid medications).
  - ii. Glucosamine and chondroitin
  - iii. Marijuana use

### **8.3. Additional co-variates of interest include:**

- age, (Assessed at baseline visit only)
- sex, (Assessed at baseline visit only)
- race / ethnicity, (Assessed at baseline visit only)
- body mass index, (Assessed at baseline visit only)
- co-morbidities, (Assessed at baseline visit only)
- a family history of hand OA, (Assessed at baseline visit only)
- occupations that they have performed in their life, (Assessed at baseline visit only)

- time spent on electronics (including smart phones, tablets, and computers) (Assessed at the baseline, week 4, week 12, and week 24 visits)
- International Physical Activity Questionnaire (iPAQ) questionnaire on physical activity, (Assessed at the baseline, week 4, week 12, and week 24 visits)
- Center for Epidemiologic Studies Depression Scale (CES-D). (Assessed at the baseline, week 4, week 12, and week 24 visits)

These data will help to assess whether randomization was successful and perhaps identify potential mediators to the effect of the traction orthosis.

